8.3 End of Treatment

The End of Treatment visit will occur within 7 days after the end of the last dose of HPN424.

If scheduled study assessments have been performed within the following windows, the assessments need not be repeated for the End of Treatment visit, unless recent clinical changes have contributed to the decision to end treatment: safety assessments (ECOG, physical exams, vital signs, ECGs, clinical laboratories) within 7 days; specialty labs (CTCs, ADA) within 3 weeks; PSA within 9 weeks; radiological imaging within 9 weeks.

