6.23.8 Progression of Underlying Malignancy

Progressive disease may be recorded as a reason for discontinuing study treatment but is not considered an AE per se and it should not be reported as an AE.

Clinical manifestations of progressive disease may be reported as AEs if they occur during the study and through the SFU (28 days [+ 7 days] after the last dose of HPN424). If clinical manifestations of disease progression meet serious criteria ([Section 6.23.5](#)), the event should be reported to the Sponsor as an SAE.

6.23.9 *Death*

Death is an outcome and not an AE per se. The event or condition that led to the patient's death should be recorded as an SAE with an outcome of fatal. If the cause of death is unknown, then "unknown cause of death" should be recorded as the SAE. If the cause of death becomes available, then the term "unknown cause of death" should be replaced with the appropriate term.

If the death can only be attributed to progression of the underlying malignancy, "progression of pre-existing cancer" should be recorded as the SAE with an outcome of fatal.

All deaths that occur after the SFU (28 days [+ 7 days] should be reported to the Sponsor.

6.24 *End of Treatment Visit*

The End of Treatment visit will occur within 7 days after the last dose of HPN424.

If the patient withdraws or is lost to follow-up and does not complete the End of Treatment visit per protocol, the Investigator will report any known AEs that occurred up to 28 days after the end of the last HPN424 infusion (i.e., through the SFU).

If scheduled study assessments have been performed within the following windows, the assessments need not be repeated for the End of Treatment visit, unless recent clinical changes have contributed to the decision to end treatment: safety assessments (ECOG, physical exams, vital signs, ECGs, clinical laboratories) within 7 days; specialty labs (CTCs, ADA) within 3 weeks; PSA within 9 weeks; radiological imaging within 9 weeks.

6.25 *Safety Follow-up*

Safety Follow-up (SFU) will occur at least 28 days (+ 7 days) after the end of the last dose of HPN424, regardless of whether the patient starts another anticancer therapy. The Investigator will report any known concomitant medications that the patient received and any known AEs that occurred through 28 days after the end of the last HPN424 infusion.

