7.1 Discontinuation of Study Treatment

Patients may continue HPN424 treatment beyond disease progression until they are no longer clinically benefiting (NLCB, per PCWG3 guidelines, [\(Scher, 2016\)](#)) as determined by the Principal Investigator and upon consultation with the Medical Monitor. For example, continuation of treatment is encouraged if a rising PSA or worsening of an isolated disease site that was not clinically significant is the sole indicator of disease progression and the patient is otherwise tolerating therapy well.

Patients (or legally acceptable representatives) may decline to continue receiving study drug at any time during the study. The primary consideration in any determination to discontinue study drug treatment is the patient's health and welfare. Patients who withdraw from study drug during the treatment period should be encouraged to return for an End of Treatment visit for evaluation of safety within 7 days of the decision to end study treatment.

The following are acceptable reasons for discontinuation of study treatment:

- Death
- Adverse event that in the Investigator's or Sponsor's judgement warrants withdrawal of study treatment
- Withdrawal of consent
- Serious violation of the study protocol (including persistent patient attendance failure or persistent non-compliance)
- Sponsor's decision to terminate the study
- Withdrawal by the Investigator for clinical reasons not related to HPN424
- Documented progressive disease; or clinical deterioration and patient is no longer clinically benefiting (NLCB) as determined by the Principal Investigator

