7.5 Replacement of Study Patients

Patients in the Dose Escalation stage who do not receive at least 3 Target doses of HPN424 for reasons other than DLT at the Target Dose (e.g., logistical or technical reasons, non-DLT-related dose delays, or toxicity at a Priming Dose level which inhibits escalation to the Target Dose) may be replaced for DLT evaluation purposes but can remain on study and receive

additional treatment with HPN424 per protocol. Patients in Dose Escalation who withdraw for any reason after the DLT period will not be replaced.

Patients in Dose Expansion who withdraw due to documented disease progression or unacceptable treatment-related toxicity will not be replaced. Patients withdrawing for other reasons may be replaced, on a case by case basis, after discussion with the Medical Monitor.

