- ^a Long-term follow-up telephone calls or visits to occur monthly (± 7 d) for 6 months, then every 3 months (± 1 month) until death, lost to follow-up, or withdrawal from study.
- ^b Predose assessments are to be done on the day of, and prior to, the start of infusion, unless otherwise indicated. C1D1 predose assessment must be completed within 72 hours prior to start of the C1D1 dose of HPN424, unless otherwise indicated. If Screening assessments were not done within this window, they need to be repeated on C1D1. C1D8+ predose assessments may be completed within 24 hours prior to the start of HPN424 infusion, provided it is after the previous dose.
- ^c Hospital admission: 48-hour inpatient admission required following C1D1 and C1D8 dosing for all patients treated at each specific dose level. All patients who undergo intrapatient dose escalation will be hospitalized for 24-hour inpatient observation following the first of each escalated dose. Please refer to [Section 5.1.4 Hospitalization and Monitoring](#) for additional instruction on requirements for hospitalization.
- ^d Informed Consent form must be signed before any study-related procedures are performed.
- ^e Height is measured at Screening only.
- ^f Full physical examination at Screening; symptom-directed exams at indicated visits thereafter.
- ^g Vital signs: blood pressure, heart rate, respiratory rate, and temperature at the following timepoints during treatment, or more often if clinically indicated: during each HPN424 dose, predose (within 1 hour prior to the start of infusion), every 15 minutes (± 10 min) during the infusion (i.e., 15, 30, 45, 60 minutes), and at 4 hours (± 1 h) after the end of infusion (EOI). For inpatients at C1D1, vital signs are to be recorded every 4 hours (± 1 h) until discharge. Beginning with Cycle 4 and beyond, the Investigator may have the option to reduce the observation period from 4 hours to ≥ 2 hours after EOI. If the observation period is reduced to ≥ 2 hours, collect vital signs 2 hours (± 30 minutes) after EOI.
- ^h Hematology: complete blood count (CBC), including platelet count and white blood cell count (WBC) with differential. C1D1 samples to be collected within 72 hours prior to dose. C1D8+ samples to be collected within 24 hours prior to dose.

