- ^b Predose assessments are to be done on the day of, and prior to, the start of infusion, unless otherwise indicated. C1D1 predose assessment must be completed within 72 hours prior to start of the C1D1 dose of HPN424, unless otherwise indicated. If Screening assessments were not done within this window, they need to be repeated on C1D1. C1D8+ predose assessments may be completed within 24 hours prior to the start of HPN424 infusion, provided it is after the previous dose.
- ^c Hospital admission: Please refer to [section 5.1.4](#) Hospitalization and Monitoring for additional instruction on requirements for hospitalization and outpatient monitoring.
- ^d Informed Consent form must be signed before any study-related procedures are performed.
- ^e Height is measured at Screening only.
- ^f Full physical examination at Screening; symptom-directed exams at indicated visits thereafter.
- ^g Vital signs: blood pressure, heart rate, respiratory rate, and temperature at the following timepoints during treatment, or more often if clinically indicated: during each HPN424 dose, predose (within 1 hour prior to the start of infusion), every 15 minutes (± 10 min) during the infusion (i.e., 15, 30, 45, 60 minutes), and at 4 hours (± 1 h) after the end of infusion (EOI). For inpatients at C1D1 and C1D8, vital signs are to be recorded every 4 hours (± 1 h) until discharge. Beginning with Cycle 4 and beyond, the Investigator may have the option to reduce the observation period from 4 hours to ≥ 2 hours after EOI. If the observation period is reduced to ≥ 2 hours, collect vital signs 2 hours (± 30 minutes) after EOI.
- ^h Hematology: complete blood count (CBC), including platelet count and white blood cell count (WBC) with differential. C1D1 samples to be collected within 72 hours prior to HPN424 administration. C1D8+ samples to be collected within 24 hours prior to HPN424 administration. During 48-hour inpatient hospitalization, should be drawn once within 24-hour period after HPN424 administration, and once during 24-48-hour period after HPN424 administration.

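### The End of Treatment waiver does not require a sample taken after the last dose, so pre-dose blood can replace the only scheduled blood count and full chemistry that would follow it

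*Protocol*

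**What the plan says.** On timing, Section 6.24 states: "The End of Treatment visit will occur within 7 days after the last dose of HPN424". Section 8.3 repeats it: "The End of Treatment visit will occur within 7 days after the end of the last dose of HPN424". Both sections then list tests that need not be repeated at that visit, among them "safety assessments (ECOG, physical exams, vital signs, ECGs, clinical laboratories) within 7 days". The one exception is that the waiver applies "unless recent clinical changes have contributed to the decision to end treatment". Neither section says that the accepted test must have been done after the last dose.

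Routine blood is taken before dosing. For Fixed Dosing, footnote h of Appendix 1 reads: "C1D8+ samples to be collected within 24 hours prior to dose". For Step Dosing, Appendix 2 reads: "C1D8+ samples to be collected within 24 hours prior to HPN424 administration". The chemistry footnotes say the same and add a four-analyte liver panel shortly after dosing and at 5 hours on C1D1, C1D8 and C1D15.

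Sections 6.25 and 8.4 name no laboratory test for the Safety Follow-up visit. Section 6.25 mentions only concomitant medications and adverse events.

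Section 7.1 uses another anchor. It encourages patients who withdraw from study drug to "return for an End of Treatment visit for evaluation of safety within 7 days of the decision to end study treatment".

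**The concern.** A sample drawn before a dose cannot show what that dose did. The EOT blood count and chemistry are the scheduled look at the effect of the final dose, yet the 7-day look-back is as long as the window for the visit. On some dosing days the pre-dose sample therefore falls inside the look-back at almost any permitted visit.

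Two outputs are exposed. Several dose-limiting toxicities (DLTs) in Section 5.2 are defined wholly or partly by laboratory values: Grade 4 thrombocytopenia, Grade 4 neutropenia lasting more than 5 days, and Hy's Law. DLTs are the primary endpoint of Dose Escalation. SAP Section 10.5 tabulates shifts to the maximum post-baseline grade, and that maximum can only come from samples that were taken.

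**Working it through.** The plan gives no figure to reproduce, so the check is interval arithmetic.

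**Inputs**
- Last dose on day 0; EOT visit on day t, with t from 0 to 7 (6.24, 8.3).
- Look-back of 7 days. The text gives no reference point; I count it back from the EOT visit.
- Pre-dose sample on day s. For a dose that is itself on a laboratory day, s = 0 or s = −1 (Appendices 1 to 4).
- Weekly dosing with at least 4 non-dose days between doses (5.1.2.4, 5.1.3.4), so the shortest gap is 5 days.

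**Rule:** the waiver is met when t − s ≤ 7.

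| Last dose | Latest pre-dose laboratories, s | EOT days on which the waiver is met |
|---|---|---|
| On a laboratory day, drawn the same day | 0 | 0 to 7 |
| On a laboratory day, drawn the day before | −1 | 0 to 6 |
| Day 8, Cycle 3 or later, nominal gap | −7 | 0 only |
| Day 8, Cycle 3 or later, shortest gap | −5 | 0 to 2 |
| Day 15, Cycle 3 or later, nominal gap | −14 | none |

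**Which last doses are exposed.** These are laboratory days with no next-day draw.
- *Cycle 1, Days 1 and 8:* the available grids show laboratories on the following days, so these doses are largely covered.
- *C1D15, Fixed Dosing:* the Fixed SC grid has no count between C1D15 and C2D1. The Fixed IV grid (Appendix 1) is not in the text available to me; its footnotes give only pre-dose draws plus the liver panels.
- *Cycle 2, Step arms:* laboratories are weekly and pre-dose. Where the patient is admitted (Table 15 lists C2D1 for two priming doses, and C2D1 and C2D8 for three), the footnotes add draws in the first and second 24 hours. The other Cycle 2 visits are exposed.
- *Cycle 3 onward:* mainly Day 1, hardly Day 8, not Day 15.

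**No later draw.** In Appendix 2 the single post-treatment hematology mark lines up with the ECG and PSA marks, which the footnotes place at EOT. EOT is therefore the only scheduled count and full chemistry after these doses.

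**The C1D15 case.** Target Doses on Days 1, 8 and 15 make three. Section 7.5 offers replacement to "Patients in the Dose Escalation stage who do not receive at least 3 Target doses of HPN424 for reasons other than DLT", so this patient is outside that rule. The Fixed Dosing DLT period is D1 to D21 (Table 15), leaving 21 − 15 = 6 days. A patient who continues has the C2D1 pre-dose sample, nominally Day 22 or up to 24 hours earlier. A patient who stops has only the EOT draw, due by 15 + 7 = Day 22, and the Day 15 pre-dose sample can waive it.

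**Anchor.** Suppose the next dose, due on day 7, is held for the 3 weeks that Section 5.3 permits, and treatment is then stopped on day 7 + 21 = 28. EOT is due by day 7 under 8.3 and by 28 + 7 = day 35 under 7.1. The schedule grids also show a '+7d' window in the EOT column.

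**The case against.** The case for leaving the text alone has real substance.

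- *Other blood remains.* A reader might infer that no blood at all follows the last dose. That is wrong. PK and ADA samples are scheduled at EOT and PK is not on the waiver list. Table 16 adds PK and cytokine samples after the C1D15 infusion, the Cycle 1 same-day liver panels stand, and symptoms can prompt tests. Only the scheduled blood count and full chemistry are at issue.
- *The 6 days are not caused by the waiver.* Continuing patients also have essentially no scheduled count on Days 16 to 21. What the waiver can remove is the one sample that would close the period for a patient who stops.
- *DLT-free status is not stated.* It is tempting to say that such a patient counts as free of DLT. Sections 5.2 and 7.5 say who may be replaced, not that three doses suffice for evaluability. Section 3.1.1 requires observation through 21 days after the first Target Dose, with committee review before escalation.
- *The waiver has a brake.* It lapses when recent clinical changes contributed to stopping. Section 5.4.3 reports that most high-grade transaminitis followed the initial dose or initial step-up.
- *Late visits escape.* With EOT on day 8 or later, a dosing-day sample is more than 7 days old and no longer qualifies.

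All of these limit the point. None supplies a required count or chemistry after the last dose for a patient with a silent change who stops for another reason.

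**Conclusion.** The gap is real but narrow. As written, pre-dose blood can replace the only scheduled count and full chemistry after a last dose on C1D15 in Fixed Dosing, at non-admission Cycle 2 visits in the Step arms, or on Day 1 from Cycle 3. This applies on EOT days 0 to 6, and on day 7 with a same-day draw. A silent laboratory-defined DLT could then go unseen, and the SAP 10.5 maximum may omit the last dose's effect.

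The frequency cannot be derived. A figure of about 1 in 3 last doses from Cycle 3 would need last doses spread evenly over Days 1, 8 and 15, which the documents do not give. One patient is 1/3 = 33% of a 3-patient cohort or 1/6 = 17% of a 6-patient cohort; that is the patient's weight in the decision, not a risk estimate. Nor does the gap cover every last dose in Cycle 1, because next-day laboratories follow C1D1 and C1D8 in the available grids.

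The conclusion rests on counting the look-back from the EOT visit, on grids that are partly broken, and, for Fixed IV, on footnotes alone. The anchor conflict is a separate wording matter.

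**What to change.** In Sections 6.24 and 8.3, let an earlier safety assessment stand in for the EOT assessment only if it was done on a calendar day after the last HPN424 dose and within 7 days of the EOT visit. The calendar-day wording matters: if the text required only a test after the last dose, the C1D15 panels at about 15 minutes and 5 hours would still waive the EOT liver tests. The cost is one clause in two sections and fewer waived tests, all of them already scheduled at EOT.

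Separately, reconcile the timing of the EOT visit across 6.24 and 8.3 (last dose), 7.1 (decision to end treatment) and the '+7d' window in the schedules.

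SAP Section 3 records that the sponsor decided to discontinue the study during Dose Escalation in March 2022, so the protocol wording now matters mainly for reuse. In the synoptic report, flag patients with no hematology or chemistry result dated after the day of their last dose, in the laboratory shift tables and alongside the DLT listing. This needs only dates already in the database.

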8.4 Safety Follow-up

Safety Follow-up (SFU) visit will occur at least 28 days (+ 7 days) after the end of the last dose of HPN424, regardless of the reason for stopping treatment and should occur even if the patient starts another anticancer therapy.

8.5 Long Term Follow-up Visits and End of Study Participation

After the SFU, patients are to be contacted via telephone or during routine clinic visits to determine survival. These long-term follow-up (LTFU) telephone calls or visits are to occur monthly (± 7 days) for 6 months following the SFU, then every 3 months (± 1 month) until death, lost to follow-up or withdrawal from study.

9 QUALITY CONTROL AND ASSURANCE

The following steps will be taken to ensure the accuracy, consistency, completeness, and reliability of the data:

- Training of site personnel on all protocol procedures during site initiation visits
- Routine study site monitoring ([Section 11.6](#))
- CRF review against source documents ([Section 11.8](#))
- Data management quality control checks ([Section 11.10](#))

In addition, the Sponsor or designee may conduct periodic site audits.

10 PLANNED STATISTICAL METHODS

10.1 General Considerations

Descriptive statistics will be used to summarize data including baseline patient characteristics, treatment with HPN424, safety variables and preliminary efficacy. Categorical or nominal variables will be summarized by frequency and percentage. Continuous variables will be summarized using standard summary statistics (n, mean, standard deviation, median, minimum, and maximum). Where appropriate, 95% confidence intervals around point estimates will be presented. Details of endpoints analyses will be described in the Statistical Analysis Plan.

No imputation of values for missing data will be performed except that missing or partial start and end dates for AEs and concomitant medication will be imputed according to prespecified, conservative imputation rules. Patients who withdraw or are lost to follow-up will be included in statistical analyses to the point of their last evaluation.

10.2 Determination of Sample Size

Up to 150 patients with mCRPC may be enrolled. The number of cohorts and patients will depend on data observed during Dose Escalation.

Dose Escalation may include up to 130 patients, depending on the dose at which the MTD and RP2D(s) are determined. The sample size and design of the Dose Escalation portion of the study are consistent with those in other oncology studies used to determine MTD. The traditional 3 + 3 dose escalation scheme employs the standard NCI definition of MTD (highest dose associated with DLT in <33.3% of patients) for each arm.

Dose Expansion will include up to 20 evaluable patients using a Simon 2-stage design to assess preliminary clinical efficacy of HPN424 at the RP2D(s). Power calculations based on a Simon 2-stage minimax design ([Simon, 1989](#)) test the null hypothesis that overall response rate (ORR) ≤ 0.01 versus the alternative hypothesis that ORR ≥ 0.15 , with a Type 1 error rate of 0.05 and power of 80%. This design would allow identification of a target response rate of 15% or better in a population of patients who have failed standard available therapy and would not be expected to have any responders.

A sample size of 14 evaluable patients will be enrolled in the first stage. If the total number responding (defined as partial response [PR] or complete response [CR] is ≥ 1 , an additional 6 evaluable patients will be enrolled in the second stage for a total of 20 evaluable patients. If the total number responding is ≤ 1 , the effectiveness of treatment based on ORR will be rejected. If treatment is actually not effective and ORR 0.01, then the expected sample size is 14.8 evaluable patients with a 0.869 probability of early termination and there is a 0.016 probability of incorrectly concluding the treatment is effective (the target for this Type 1 error rate was 0.05 or less). If the treatment is actually effective, there is a 0.199 probability of incorrectly concluding it is not effective (the target for this Type 2 error rate was 0.20 or less).

While the intention is to study a single RP2D, additional expansion cohorts of up to 20 patients per expansion cohort may be added at the recommendation of the CRC. If the CRC recommends multiple RP2Ds, each will be evaluated with independent Simon 2-stage designs of up to 20 evaluable patients per RP2D.

10.3 Analysis Populations

Safety analyses will be based on the Safety Population, defined as all patients who have received any amount of HPN424.

Efficacy analyses will be performed based on the Efficacy Evaluable Population, defined as all patients who have received any amount of HPN424 at the assigned RP2D and who have any evaluable post baseline disease assessment. Patients who withdraw from study treatment due to clinical progression or death without post baseline assessments will be considered non-responders.

PK analyses will be based on the PK Evaluable Population, defined as all patients who have received any amount of HPN424 and who have any evaluable post baseline PK assessment.

10.4 Study Endpoints

10.4.1 Primary Endpoints

Dose Escalation:

- Number and severity of DLTs following treatment with escalating doses of HPN424.

Dose Expansion:

- Overall response rate (ORR), as assessed by PCWG3 criteria for response.

